CLINICAL STUDY PROTOCOL

Screening for Colorectal Neoplasms with the Fecal Testing: a Population-based Randomized Study

Protocol Number: 201205030RIB

ClinicalTrial.gov Number: NCT 01741363

Indication:	Colorectal Neoplasms
Principal Investigator:	[name]., Ph.D.
Version Number:	V1.0
Date	May-30-2012
Funding Support:	Health Promotion Administration, Ministry of Health and Welfare

All the information disclosed or provided by the Health Promotion Administration, Ministry of Health and Welfare or produced during the clinical trial, including this protocol, the CRFs, the Investigator Brochure, and the results obtained during the clinical trial, is confidential and is intended for the use of clinical investigators, and any person under his/her authority agree to keep confidential.

ABSTRACT

Screening for stomach diseases and colorectal neoplasms with the fecal testing: a population-based randomized study

Growing body of evidences have shown that fecal immune test (FIT) outperform guaiac fecal occult blood test (gFOBT) in terms of sensitivity, neoplasm detection rate and public participation. Though direct outcome evidence is still lacking for FIT, it is anticipated to have higher colorectal cancer (CRC) mortality and incidence reduction compared with gFOBT. In Taiwan, nation-wide CRC screening program has been launched since the year of 2004 ,which provides biennial FIT screening for adults aged 50 to 75 years. Currently available data from the Bureau of Health Promotion has shown a significant stage-shift effect, an early indicator of screening effectiveness, by this screening program.

Nevertheless the aforementioned advantages of FIT, missed neoplasms and interval cancer still exists under the current one-day stool sampling method with biennial screening interval, which might affect the effectiveness of overall screening program. Increase the number of stool samples or shortening of screening interval may be helpful for early detection of clinically significant neoplasms but it remains unclear whether such an approach may lower the screenee compliance or public participation. Moreover, its impact on the demand of confirmatory colonoscopy and cost-effectiveness of the whole screening program is still largely unknown and need to be further investigated.

In this study, we aim to randomly allocate screening attendee to one of the

following four arms: one-day sampling with annual screening, one-day sampling with biennial screening, two-day sampling with annual screening, and two-day sampling with biennial screening. Participation rate, positive rates of FIT, detection rate for neoplasms, positive predictive value, and long-term outcome including cancer incidence and mortality will be calculated and compared among four groups. In addition, cost-effectiveness analysis will be also conducted using previously established Markov model of CRC natural history using the results ascertained from this trial.

The abundant results from this trial will be helpful for assessing the feasibility of increasing stool sampling and shortening screening interval in population setting, their long-term effects, and cost-effectiveness.

However, in Taiwan, although the incidence of colorectal cancer is rapidly increasing, *Helicobacter pylori*-related upper GI pathologies remain highly prevalent, which may imply that mass screening solely based on FIT could be insufficient as significant upper GI pathologies can be missed. Since FIT does not predict upper GI pathologies, the adjuncts of *H. pylori* stool-antigen test (HpSA) may be a potential candidate to realize a pan-detecting assay based on stool samples in a population in which both lower and upper GI lesions are equally prevalent.

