## 1.4 Study groups, randomisation, and stratification

Subjects who meet inclusion/exclusion criteria will be randomized to 4 groups in

Confidential

this stratified, clustered randomized trial:

1. FIT one-day sampling with one-year interval
2. FIT one-day sampling with two-year interval
3. FIT two-day sampling with one-year interval
4. FIT two-day sampling with two-year interval

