## **1.5 Sample size calculation**

Sample size estimation will be conducted based on literature review and empirical data from our national program. We are assuming colorectal cancer detection rate of 2.4/1000 by one-sample FIT and 4.8/1000 by two-sample FIT with a FIT screening uptake rate of 60% in both arms, 80% power and one-tail significant level at 0.05, also taking into account cluster size of 65 (The total number of townships in Changhua, Tainan and Kaohsiung) with inter-cluster correlation coefficient of 0.01, the estimated sample size is 14,625 subjects for each arm.

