## **1.6 Selecting and inviting the population to be screened**

Initially, men and women between the ages of 50 and 69 will be identified and screened for eligibility and interest. Those who fulfill the eligibility criteria and are interested will be recruited into the trial and must provide a signed informed consent form. Participants will be randomly assigned into one of two study arms: the one-day sampling group and the two-day sampling group. Baseline data collection for participants in both arms of the trial includes completion of a questionnaire which collects basic demographic data and risk factor information. Invitation list will be generated by each site, based on the household registry in the individual region.

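### Does the plan need to name the one-day versus two-day cancer detection contrast as its analysis, because the protocol speaks only of comparing four groups?

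*Protocol*

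**What the plan says.** The protocol abstract sets out a two-by-two design, sampling days (one or two) by screening interval (annual or biennial). It then lists participation, FIT positivity and further outcomes, of which "detection rate for neoplasms, positive predictive value, and long-term outcome including cancer incidence and mortality will be calculated and compared among four groups". It values the results for "assessing the feasibility of increasing stool sampling and shortening screening interval in population setting", so both factors matter to the sponsor.

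SAP 1.4 lists the same four groups and calls the study "this stratified, clustered randomized trial". SAP 1.5 sizes a single contrast: "colorectal cancer detection rate of 2.4/1000 by one-sample FIT and 4.8/1000 by two-sample FIT". The remaining design values given there include "FIT screening uptake rate of 60% in both arms, 80% power and one-tail significant level at 0.05", and the section concludes that "the estimated sample size is 14,625 subjects for each arm". SAP 1.6 uses the same two-way split: "Participants will be randomly assigned into one of two study arms: the one-day sampling group and the two-day sampling group".

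Sections 1.1 to 1.9 cover design, region, population, groups, size, invitation, FIT, colonoscopy and quality assurance. None names a test, a model or a primary analysis. The design figure is not reproduced in the text available and may add detail.

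**The concern.** The sample size rests on a two-group question about cancer, whereas the only comparison of outcomes stated in words has four groups and names neoplasms. The abstract's sentence could mean a main effect of sampling days pooled over interval, pairwise comparisons, or one overall test with 3 degrees of freedom. It gives no round, denominator or direction.

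The readings differ in power. At the first round, groups that differ only in interval receive the same test, so an overall four-group test of first-round detection spends degrees of freedom on differences expected to be nil. If the contrast, denominator and sidedness were all open, they could be settled after the data were seen.

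**Working it through.** **1. The plan's own figure.** Inputs from SAP 1.5: p1 = 0.0024, p2 = 0.0048, one-sided 0.05 (z = 1.645), 80% power (z = 0.842), uptake 0.60, ICC 0.01, and 65 used as cluster size.

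- Screened per arm: (1.645 + 0.842)² × (0.0024 × 0.9976 + 0.0048 × 0.9952) / 0.0024² = 6.183 × 0.0071712 / 0.00000576 ≈ 7,697.
- Divided by uptake: 7,697 / 0.60 ≈ 12,829.
- Design effect: 1 + (65 − 1) × 0.01 = 1.64, giving about 21,039 per arm.

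The stated 14,625 is not reproduced; 21,039 is 44% higher. That is a fault of the sample size section, and naming an analysis would not repair it.

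**2. What 1.5 already settles.**

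| Item | Settled in 1.5? |
|---|---|
| Endpoint | Yes: colorectal cancer detection |
| Contrast | Yes: one-sample against two-sample FIT |
| Level and direction | Yes: 0.05, one-sided |
| Denominator | Implied: with uptake entered separately, the rates appear to be per person screened |
| Round, pooling over interval, method for clusters | No |

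**3. Power under each reading.** No section specifies a test, so this is illustrative. Assume four equal groups and SAP 1.5's cancer rates (no neoplasm rate is given). Let n be screened persons per group divided by the design effect, and L = 4n × 0.0012² / (0.0036 × 0.9964).

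- Pooled contrast, one-sided: Φ(√L − 1.645).
- Two-day against one-day within one interval, one-sided: Φ(√(L/2) − 1.645).
- Overall test: noncentral chi-square, 3 df, noncentrality L, level 0.05.

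Example: 14,625 × 0.6 = 8,775 screened; 8,775 / 1.64 = 5,351; L = 8.59. Pooled: Φ(2.931 − 1.645) = 90.1%. Within one interval: Φ(2.073 − 1.645) = 66.6%.

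| 14,625 is per | Design effect | L | Pooled | Within one interval | 3-df |
|---|---|---|---|---|---|
| each of four groups | 1.64 | 8.59 | 90.1% | 66.6% | 68.9% |
| sampling group | 1.64 | 4.30 | 66.6% | 42.9% | 38.3% |
| each of four groups | 1 | 14.09 | 98.3% | 84.4% | 89.8% |
| sampling group | 1 | 7.05 | 84.4% | 59.2% | 59.3% |
| each of four groups | 6.39 | 2.21 | 43.6% | 27.6% | 20.9% |
| sampling group | 3.69 | 1.91 | 39.6% | 25.2% | 18.5% |

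The last two rows take 65 as the number of randomised townships: 4 × 8,775 / 65 = 540 screened per township, or 270 if 14,625 is per sampling group; 1 + 539 × 0.01 = 6.39 and 1 + 269 × 0.01 = 3.69.

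For 80% power, L must be 10.90 (3-df), 7.85 (two-sided contrast) or 6.18 (one-sided contrast). The overall test therefore needs 10.90 / 7.85 = 1.39 times the people of a two-sided contrast, and 10.90 / 6.18 = 1.76 times those of the one-sided contrast in 1.5.

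**4. Does pairwise testing fall short of the sized question?** If 14,625 is per each of four groups, a two-day against one-day comparison within one interval sets 14,625 against 14,625, which is the contrast in 1.5. Pooling then adds power beyond what was planned. Only if 14,625 is per sampling group does the pairwise test fall below plan.

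**5. Denominator.** With the pooled-variance formula and no design effect, per person screened gives 7,700 / 0.6 = 12,834 allocated per arm. Counting per person allocated, with rates diluted to 0.00144 and 0.00288, gives 12,852. The difference is 18 people, so at the equal uptake that 1.5 assumes the choice barely affects power.

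**The case for a change.** The strongest case for a change is that a document headed as an analysis plan should state an analysis. Planning assumptions are not a commitment, and 1.6 describes allocation rather than analysis. One sentence would close the gap, and the pooled contrast has the most power in every row of the table.

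Much of this stands. The explicit link is absent, and so are the round and the way in which clustering is handled. A sentence tying the analysis to 1.5 would do no harm.

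Two parts do not stand. First, endpoint, contrast, level and direction are not open: 1.5 put them on record in advance, so an analyst who departed from them would have to explain why. Second, the large power loss belongs to a 3-df test that no section proposes; comparing outcomes among four groups is ordinary abstract language and also covers a two-by-two analysis.

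A fuller rewrite also has costs. Making the first round primary and counting per person allocated are choices found nowhere in the documents. Ranking interval second does not follow from an abstract that names both factors side by side. Reducing the four-group comparison of participation to description would weaken an analysis already planned, although the abstract treats participation as an open question.

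**Conclusion.** No change follows. This is missing detail that analysts would fill sensibly: they would test the contrast sized in 1.5 and allow for the clustered, stratified design stated in 1.4. A four-group comparison would remain a valid, if less powerful, analysis.

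At a design effect of 1.64, choosing the within-interval comparison over the pooled one costs about 24 percentage points of one-sided power under either meaning of arm (90.1 − 66.6 = 23.5; 66.6 − 42.9 = 23.7). For the pooled contrast alone, the unresolved meanings of arm and 65 move power from about 40% to 98%. That uncertainty matters more and belongs to the sample size section.

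The conclusion assumes that analysts follow the direction and endpoint in 1.5, that the four groups are of equal size, and that uptake is the same in all of them. If uptake differed between one-day and two-day sampling, the screened and allocated denominators would answer different questions and both would need to be shown.

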[figure not shown]

# 1. Statistical Analysis Plan

## 1.1 Study type

This study is a community-based clustered randomized controlled trial. The study design (**Figure 4- 1**) is shown as follows:

**Figure 4- 1 Schematic diagram of the study design**

## 1.2 Scope

The study will be conducted in three different regions of Taiwan: Changhua, Tainan, and Kaohsiung.

## 1.3 Target population

The study is a population-based cluster-randomized trial. Participants aged between 50 and 69 will be invited to take the screening test and will be randomly allocated each study arms.

## 1.4 Study groups, randomisation, and stratification

Subjects who meet inclusion/exclusion criteria will be randomized to 4 groups in

Confidential

this stratified, clustered randomized trial:

1. FIT one-day sampling with one-year interval
2. FIT one-day sampling with two-year interval
3. FIT two-day sampling with one-year interval
4. FIT two-day sampling with two-year interval

## **1.5 Sample size calculation**

Sample size estimation will be conducted based on literature review and empirical data from our national program. We are assuming colorectal cancer detection rate of 2.4/1000 by one-sample FIT and 4.8/1000 by two-sample FIT with a FIT screening uptake rate of 60% in both arms, 80% power and one-tail significant level at 0.05, also taking into account cluster size of 65 (The total number of townships in Changhua, Tainan and Kaohsiung) with inter-cluster correlation coefficient of 0.01, the estimated sample size is 14,625 subjects for each arm.

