## **1.7 Determination of fecal occult blood**

Quantitative FIT (OC-SENSOR by Eiken Chemical Co., Ltd., Tokyo, Japan,) with fecal hemoglobin cutoff of 100 ng/ml (equivalent to 20 µg hemoglobin/g feces) will be used in this trial. The mass of feces collected and volume of the device buffer were claimed as 10 mg and 2 mL by the manufacturer. Reading of the FIT

Confidential

tests will be done in a centralized manner in each region. Individuals will be advised to collect the fecal sample at home using the collecting stick and return the completed kit within a week, and maintaining it in their refrigerator until such a moment. A positive test for one-sample group will be defined as a result that is above the defined cutoff and a positive test for two-sample group will be defined as positive of any one of the two samples. Those who come up positive FIT will then be referred for verification colonoscopy.

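### SAP 1.5 ties its only power figure to a doubling of cancer detection, which is the ceiling under the SAP's own positivity rule, and gives no power for a smaller gain

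*SAP*

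**What the plan says.** SAP 1.5 assumes a "colorectal cancer detection rate of 2.4/1000 by one-sample FIT and 4.8/1000 by two-sample FIT", so the second sample is taken to double the yield. The remaining design inputs in that section are these: "FIT screening uptake rate of 60% in both arms, 80% power and one-tail significant level at 0.05". It allows for a "cluster size of 65 (The total number of townships in Changhua, Tainan and Kaohsiung) with inter-cluster correlation coefficient of 0.01" and arrives at 14,625 subjects per arm. The basis is given in general terms: "Sample size estimation will be conducted based on literature review and empirical data from our national program". No figure from those sources is shown, and no other effect size or power appears in the supplied text.

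SAP 1.7 sets a single "fecal hemoglobin cutoff of 100 ng/ml" and says that "a positive test for two-sample group will be defined as positive of any one of the two samples". Positives are referred for colonoscopy in either group; no completion rate is given.

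The number of arms differs between sections. SAP 1.6 has participants "randomly assigned into one of two study arms: the one-day sampling group and the two-day sampling group". SAP 1.4 has "Subjects who meet inclusion/exclusion criteria will be randomized to 4 groups in" a stratified cluster design, crossing sampling days with screening interval. It is therefore unclear whether 14,625 is the size of one of two arms or one of four groups.

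**The concern.** Two samples from the same person, read by the same assay at the same cutoff, will tend to find some of the same cancers. A cancer that is positive on both days adds nothing to the yield of the second sample. A doubling leaves no room for any such overlap.

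Cancer detection is the only outcome for which the documents give a sample size, so the 80% in SAP 1.5 is the only statement of what the trial can show. If it holds only at the most favourable value that the positivity rule allows, a reader may take a non-significant result as evidence that a second sample adds little, when a worthwhile gain could easily have been missed. The point concerns the cancer-detection comparison only, not the other outcomes listed in the Protocol abstract.

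**Working it through.** **The plan's own figure.** Inputs from SAP 1.5: p1 = 0.0024, p2 = 0.0048, one-sided 5%, 80% power, uptake 0.6. Effective number screened per arm:

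n = (1.645 + 0.842)² × (0.0024 × 0.9976 + 0.0048 × 0.9952) / 0.0024² ≈ 7,697.

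- Literal clustering inputs (cluster size 65, ICC 0.01): design effect 1 + 64 × 0.01 = 1.64, and 7,697 × 1.64 / 0.6 ≈ 21,039 per arm, not 14,625.
- 65 clusters per arm with ICC 0.01: no solution, since the effective number cannot exceed 65 / 0.01 = 6,500.
- 65 clusters per arm with ICC 0.001: 65m / (1 + (m − 1) × 0.001) = 7,697 gives m = 134.2, rounded up to 135; 65 × 135 / 0.6 = 14,625 exactly. This is an inference and departs from the stated ICC.

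The stated inputs therefore do not reproduce 14,625. That is a separate clustering question. The ceiling below does not depend on it.

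**The ceiling.** Let s be the cancer yield of one sample and c the share of cancers positive on one sample that are also positive on the other. Then

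P(A or B) = 2s − P(A and B) = s(2 − c), so the ratio is 2 − c ≤ 2.

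The SAP supplies the single cutoff, the rule that either sample suffices, and equal uptake. Equal yield per sample and equal colonoscopy completion are assumptions made here. With s = 2.4 per 1000:

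| c | Ratio | Two-sample rate per 1000 |
|---|---|---|
| 0 | 2.0 | 4.80 |
| 0.3 | 1.7 | 4.08 |
| 0.5 | 1.5 | 3.60 |
| 0.7 | 1.3 | 3.12 |

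The values of c are illustrative.

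**Power of the existing sample.** Power = Φ((p2 − p1) / √((p1q1 + p2q2) / n) − 1.645), with q = 1 − p and n the effective number screened per side. Rates are taken per person screened, which SAP 1.5 does not state. Screened per arm: 14,625 × 0.6 = 8,775; for two groups pooled, 17,550.

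Example, two arms, no clustering, ratio 1.5: 0.0012 / √(0.00598128 / 8,775) = 1.453, and Φ(1.453 − 1.645) = 42%.

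| Reading of 14,625 | Effective n per side | 2.0 | 1.7 | 1.5 | 1.3 |
|---|---|---|---|---|---|
| Two arms, no clustering | 8,775 | 84% | 62% | 42% | 23% |
| Two arms, design effect 1.64 | 5,351 | 67% | 45% | 31% | 17% |
| Four groups pooled by sampling days, no clustering | 17,550 | 98% | 87% | 66% | 36% |
| Four groups pooled, design effect 1.64 | 10,701 | 90% | 70% | 48% | 26% |

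The ICC 0.001 setting (135 per cluster, design effect 1 + 134 × 0.001 = 1.134) gives 80/58/39/21% for two arms and 97/83/61/33% pooled. Taking 65 as clusters per arm with ICC 0.01 (design effect 1 + 134 × 0.01 = 2.34) gives 54/36/24/15% for two arms.

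**What drives the drop.** Holding everything else fixed, 80% power needs an effective 7,697 per side at ratio 2.0 and 25,680 at ratio 1.5, or 3.3 times as many. With 8,775 screened per arm, the expected cancers are about 21 with one sample, against 42, 36, 32 or 27 with two samples at ratios 2.0, 1.7, 1.5 or 1.3.

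**The case against.** *The sources may support the doubling.* SAP 1.5 cites literature and national programme data that are not shown, and only an abstract of the Protocol is available. This stands as far as it goes: nothing in the documents shows that the true ratio is near 1.5. But if the sources do show a ratio of 2 or more, either there is no overlap between samples or one of the conditions fails (for instance, colonoscopy completion differs), and the SAP should then say which.

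*An optimistic planning effect is a choice, and omitting a sensitivity table is not an error.* That is fair for an ordinary optimistic value. Here the value is the limit of what the positivity rule allows under those conditions, and it carries the only power figure.

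*The size of the shortfall depends on unresolved readings.* This stands. A reader might take the 31% at ratio 1.5 as the cost of assuming a doubling. The documents do not support that: under the same literal two-arm inputs, power is already 67% at ratio 2.0, and that part comes from the clustering mismatch. The effect of the ratio is seen by reading along a row of the table, not across rows.

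*The rates might be per person invited.* The uptake input makes this less likely, but it is not excluded. Four groups pooled with design effect 1.64 (29,250 / 1.64 = 17,835 per side) would then give 87% at ratio 1.7 and 67% at 1.5. Only by also ignoring clustering (29,250 per side; Φ(2.654 − 1.645)) does power at 1.5 pass 80%, at 84%. That combination leaves unused both the uptake and the clustering inputs that SAP 1.5 says were taken into account.

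**Conclusion.** The concern holds in this form: under the SAP's cutoff, positivity rule and equal uptake, with equal yield per sample and equal colonoscopy completion, 4.8 per 1000 is the highest expected two-sample rate, and the only stated power is tied to it. With rates per person screened, none of the readings reaches 80% at ratio 1.5; the most favourable, four groups pooled with no clustering, gives 66%. At ratio 1.7 the two-arm readings give 62% at best, and the pooled readings range from 70% to 87%.

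Two stronger conclusions might be inferred and are not supported. One is that a doubling is impossible: the ceiling is on the expected rate under stated conditions, and observed rates can exceed it by chance. The other is that the trial is known to be underpowered: this depends on c, which the documents do not give, and on how 14,625 is read. If it is the size of each of four groups, pooling by sampling days leaves real room, with 90% or 98% power at ratio 2.0. The algebra of the ceiling is certain given its conditions; the size of the loss is illustrative.

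**What to change.** In SAP 1.5, derive the two-sample rate from between-sample agreement in the literature or national programme data already cited, and show the figure. That means a ratio below 2 unless those data show no overlap or one of the conditions fails, in which case say so.

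Replace the unqualified 80% with the power of the existing sample at that ratio and at 1.3, 1.5 and 1.7. State with it whether the rates are per person screened or invited, the cluster size, number of clusters and ICC used, and whether 14,625 refers to each of two arms or each of four groups.

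The cost is recalculation and wording: no extra participants, no new data and no change of outcome. The downside is a less favourable stated power. The change discloses the limit and does not remove it.

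### Does SAP 1.5 need to say whether cancer detection is counted per person tested or per person randomised?

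*SAP*

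**What the plan says.** SAP 1.5 assumes a detection rate of 2.4 per 1000 with one sample and "4.8/1000 by two-sample FIT with a FIT screening uptake rate of 60% in both arms", with 80% power and a one-sided 0.05 level. It allows for clustering through a "cluster size of 65 (The total number of townships in Changhua, Tainan and Kaohsiung") and a correlation of 0.01, and concludes that "the estimated sample size is 14,625 subjects for each arm". No denominator is given for the detection rate, and no analysis set is named.

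The documents differ on who is allocated, and to how many groups:

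- **Protocol abstract:** "we aim to randomly allocate screening attendee to one of the" four arms.
- **SAP 1.3:** people aged 50 to 69 are invited to be tested and are allocated.
- **SAP 1.4:** "Subjects who meet inclusion/exclusion criteria will be randomized to 4 groups in" a stratified, clustered design.
- **SAP 1.6:** those who "are interested will be recruited into the trial and must provide a signed informed consent form"; then "Participants will be randomly assigned into one of two study arms: the one-day sampling group and the two-day sampling group".
- **SAP 1.7:** samples are taken at home and the kit is returned within a week.

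On more samples or a shorter interval, the Protocol abstract says that "it remains unclear whether such an approach may lower the screenee compliance or public participation". It lists participation, positivity, detection and positive predictive value among the outcomes to be compared across the four groups.

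**The concern.** Rates stated as being by a test, next to a separate uptake figure, read most naturally as rates per person tested. If people are allocated first and return kits afterwards, kit return is a post-randomisation event, and the Protocol itself says that the sampling scheme might affect it. Comparing only those who return kits would then give up the protection of randomisation. If fewer two-day kits come back, the ratio per person tested could stay at 2.0 while the yield per person randomised falls. With no denominator written down, the headline comparison could be chosen after the data are seen.

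**Working it through.** **Inputs.** From SAP 1.5: 2.4 and 4.8 per 1000, uptake 60% in both arms, one-sided 0.05, 80% power, correlation 0.01, the figure 65, and 14,625 per arm. Assumed, not in the documents: equal allocation, and two-day uptake of 55% or 50%.

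**1. The plan's own figure.** The pooled two-proportion formula for 2.4 against 4.8 per 1000 gives 7,700 tested per arm. Reading 65 as a cluster size, the design effect is 1 + 64 × 0.01 = 1.64.

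- Clustering only: 7,700 × 1.64 = 12,628.
- Uptake only: 7,700 / 0.6 = about 12,834.
- Both: 7,700 × 1.64 / 0.6 = 21,047.

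None of these is 14,625. The denominator does not explain the mismatch. Using rates per person randomised (2.4 × 0.6 = 1.44 and 4.8 × 0.6 = 2.88 per 1000) with the same design effect, the requirement is 21,077, against 21,047 per person tested.

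**2. Does the denominator matter at the planned uptake?** With 14,625 randomised per sampling group, 14,625 × 0.6 = 8,775 are tested. Expected cancers are 8,775 × 0.0024 = 21.06 and 8,775 × 0.0048 = 42.12. Per person randomised they are 14,625 × 0.00144 = 21.06 and 14,625 × 0.00288 = 42.12. The counts are the same and the ratio is 2.0 either way. Equal uptake rescales both groups alike.

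Power = Φ(difference / SE − 1.645), where SE² = design effect × [p₁(1−p₁)/n₁ + p₂(1−p₂)/n₂]:

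- Per person randomised: 0.00144 / 0.000695 = 2.071, power 0.665.
- Per person tested: 0.0024 / 0.001158 = 2.073, power 0.666.

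**3. What if uptake differs?** Hold one-day uptake at 60%. The ratio per person randomised is 2 × u / 0.6, where u is two-day uptake. It is 1.83 at 55% and 1.67 at 50%, against 2.00 per person tested.

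The power gap also depends on the design effect, which SAP 1.5 does not state:

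- 65 as cluster size: 1.64.
- 65 clusters in each group: 14,625 / 65 = 225, so 1 + 224 × 0.01 = 3.24.
- 65 townships in total, split between two groups: 29,250 / 65 = 450, so 1 + 449 × 0.01 = 5.49.

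Power with 14,625 randomised per sampling group, per person randomised / per person tested:

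| Design effect | Two-day uptake 60% | 55% | 50% | Gap at 50% |
|---|---|---|---|---|
| 1.64 | 0.665 / 0.666 | 0.552 / 0.644 | 0.428 / 0.619 | 0.19 |
| 3.24 | 0.432 / 0.433 | 0.352 / 0.416 | 0.273 / 0.398 | 0.12 |
| 5.49 | 0.304 / 0.304 | 0.250 / 0.293 | 0.199 / 0.281 | 0.08 |

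**4. Selection.** Suppose two-day uptake is 50%, and the 10 points of people lost have r times the detection rate of the 50 who return kits. For a true test ratio of 2, the ratio per person tested is 120 / (50 + 10r). It is 2.18 at r = 0.5 and 1.71 at r = 2. Both values of r are assumptions.

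**5. What the plan commits to.** Nothing in either document restricts the comparison to people tested. Participation and detection are both planned outcomes. If detection is reported per person tested, their product is the yield per person randomised.

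**The case for a change.** The strongest case for a change is that the omission is real and the trial is partly about participation, so the sizing assumes equality on a matter that the trial is meant to examine. SAP 1.3, 1.6 and 1.7, together with a 60% uptake input, point towards allocation before kit return. In that case a comparison over everyone allocated is the sounder headline, and saying so would cost one sentence. What 14,625 counts also matters: at a design effect of 1.64, power is about 0.67 if it counts randomised persons per sampling group and about 0.85 if it counts persons tested.

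Much of this stands as description. Neither document gives the denominator, and the texts do conflict on who is allocated and on two arms versus four. But the power difference of 0.67 against 0.85 arises at equal uptake and comes from the sample size, not from the choice of denominator, so it belongs to the separate question of how 14,625 was obtained. The harm specific to the denominator needs two further conditions: allocation before kit return, which the Protocol's reference to attendees leaves unsettled, and unequal uptake, for which the documents give no size. If only attendees are allocated, the two denominators nearly coincide. Figure 4-1, which might settle the order, is not shown in the text available.

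Prescribing an all-randomised comparison in SAP 1.5 regardless of the order would also go too far. Without a stated screening round or time window, it would leave the numerator open across annual and biennial arms.

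**Conclusion.** No change to the plan follows. The denominator is an unwritten detail, not a wrong rule. On the plan's stated inputs the two choices give the same ratio (2.0), the same expected cancers and the same power to within 0.001. An analyst can fill the gap sensibly by reporting participation, detection per person tested and detection per person allocated side by side, with the allocated comparison leading if allocation came before kit return.

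The difference becomes material only under assumed unequal uptake. At 50% two-day uptake and 14,625 randomised per group, the power gap runs from 0.08 to 0.19 across the three readings of 65, and the ratio per person randomised is 1.67. These figures assume equal allocation, allocation before kit return and the same design effect for both denominators. The failure to reproduce 14,625, the double use of 65 and the conflict between two arms and four are separate matters, and this conclusion does not clear them.
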